Study Title: Happy, Healthy, Loved: A Mobile-delivered Breastfeeding Self-efficacy Intervention for First Time Parents

NCT Number: NCT04578925

Document Date: 10/05/2020

HAPPY, HEALTHY, LOVED

Principal Investigator: [name], RNC-LRN, BSN, MBA
Riverside Methodist Hospital
Director of Women's Health Services

TABLE OF CONTENTS

- 1.0 Introduction**
- 1.1 Background
- 1.2 Theoretical Framework
- 1.3 Specific Aims/Rationale
- 2.0 Methods**
- 2.1 Study Population
- 2.2 Study Variables & Outcomes of Interest
- 2.3 Study Design
- 2.4 Statistical Analysis
- 3.0 References**

I. INTRODUCTION

Breastfeeding's health benefits are extensive and well established. For infants, health risks such as sudden infant death syndrome, infections, diabetes, obesity, and asthma (Sung et al., 2016) are lower; for mothers, breastfeeding is associated with lower risks of breast and ovarian cancers (Zhou et al., 2015). Major health organizations recommend exclusive breastfeeding for at least the first six months postpartum (Eidelman, 2012). However, exclusive breastfeeding in the US is reported by only 44.4% of women at three months postpartum (CDC) and even lower in Ohio where this study is proposed (CDC). Improving exclusive breastfeeding rates is among the nation's health priorities outlined in Healthy People 2020 (CDC). We propose a randomized trial of an affordable, scalable intervention to improve rates of exclusive breastfeeding, an important national health priority.

Theoretical Underpinnings: Targeting Breast Feeding Self-Efficacy, Partner Support and Coping. Bandura's self-efficacy, originating in social cognitive theory, is defined as confidence in one's ability to effectively perform a specific task or reach a goal (Bandura, 1977). The framework of breastfeeding self-efficacy (BSE) posits that confidence in the ability to breastfeed predicts breastfeeding effort and ability to persevere through common challenges such as latching difficulties, perceived supply concerns, and return to work (Dennis, 1999; McCarter-Spaulling & Dennis, 2010). Four sources of information are central to the development of BSE: performance accomplishments in breastfeeding, exposure to other women's breastfeeding experience, encouragement from influential others, and physiological responses to stress and anxiety (Dennis, 1999).

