The intervention emphasizes three behavioral targets: a) providing resources to support breastfeeding through modeling, information, and feedback (tailored to maternal reported breastfeeding challenges and motivations); b) providing prompts to mother and partner to communicate about support strategies (tailored to parents' preferred support behaviors); and c) providing prompts for positive evidence-based coping strategies (tailored to parents' preferred coping activities). Exclusive breastfeeding as well as breastfeeding self-efficacy will be measured at 6 weeks and 6 months as primary outcomes. Secondary outcomes of coping behaviors and perceived partner support are the behavioral targets that are hypothesized to influence the primary outcomes of BSE and exclusive breast feeding and will also be measured at 6 weeks and 6 months. Because the intervention emphasizes coping strategies for managing stress, we hypothesize that baseline cortisol will act as a moderator for the intervention, with mothers experiencing elevated cortisol benefitting the most from the intervention.

In 2017, we conducted a small pilot study to test the feasibility of our HHL program. We enrolled 17 mothers and 10 partners to complete the baseline assessments and then randomly assigned them to the HHL group (n=8 mothers) or usual care (n= 8 mothers). Follow-up rates at 6-weeks postpartum were 94% for mothers and 90% for partners. Mothers and partners who completed the HHL intervention (n=12) rated the acceptability of the program on a five-point agreement scale. The majority of parents agreed or strongly agreed that the program was beneficial (83%) and that participating was manageable (91.7%). No parents opted to stop receiving messages during the six-week delivery.

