Edinburgh Postnatal Depression Scale (Cox, Holden, & Sagovsky, 1987). The EPDS is a well-validated 10-item self-report depression screening tool, in which endorsement of each item is based on how women feel during the previous 7 days. Possible scores range from 0 to 30, with high scores reflecting more depressive symptoms. The EPDS has shown high sensitivity, specificity, and positive predictive power for postpartum depression when using the 10+ score cutoff (Dennis & Ross, 2006; Zekowitz & Milet, 1995). Across a variety of studies with women, consistency has been at acceptable levels (Cronbach's alpha .73--.87, test-retest .53--.74; (Boyd, Le, & Somberg, 2005). The EPDS has also been validated as an acceptable screening tool for men in the postpartum period (Edmondson, Psychogiou, Vlachos, Netsi, & Ramchandani, 2010; Matthey, Barnett, Kavanagh, & Howie, 2001).

Maternal Mood Screener (Munoz, 1998). The mood screener questions were adapted from the Diagnostic Interview Schedule (Robins, Helzer, Croughan, & Ratcliff, 1981) and assesses lifetime and current major depressive episode. Positive endorsement of 5 out of 9 depression symptoms present for at least two weeks screens positive for possible major depressive episode. The screener is a self-report checklist using DSM-IV criteria that has shown high (kappa = .76) concordance with the SCID-CV, the gold standard diagnostic interview for depression (Vázquez, Muñoz, Blanco, & López, 2008). The assessment for lifetime and current major depressive episodes will be administered at 0-2 days post-partum and only the assessment for current episodes will be administered at the 6 week and 6 month follow-up time points.

Depression Anxiety and Stress Scales (DASS-21). The DASS-21 will be used to measure the unique symptoms of each state. There is normative data for the scale, and the depression and anxiety subscales have shown high convergent validity with the Beck Depression Inventory and Beck Anxiety Inventory (Antony, Bieling, Cox, Enns, & Swinson, 1998).

Index of Breastfeeding Status. Rather than conceptualizing breastfeeding as a dichotomous outcome, participants' level of breastfeeding exclusivity will be measured as a continuous variable differentiating among exclusive, partial, and token breastfeeding as suggested by previous authors (Labbok & Coffin, 1997) Women will be asked to identify the

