level that accurately described their breastfeeding behaviors within the previous 24 hours. Four levels will be reported: exclusive breastfeeding (breast milk only), partial breastfeeding (breast milk and at least 1 bottle of formula per day), token breastfeeding (breast given to comfort baby not for nutrition), and no breastfeeding. Higher values represent more exclusive breastfeeding. This measure has been successfully used at RMH in previous research (Henshaw et al, 2015).

Breastfeeding Self-Efficacy Scale-Short Form (McCarter-Spaulding & Dennis, 2010). The BSES-SF has demonstrated strong reliability and validity and will be used to measure BSE. Higher scores indicate greater self-efficacy related to breastfeeding. High internal consistency has been demonstrated in previous samples (Cronbach's $\alpha=.91$; (Henshaw et al., 2015). A wording change to measure self-efficacy in the supportive partner role has also been validated (Dennis, Brennenstuhl, & Abbass-Dick, 2018) and will be used for the partner survey.

Brief COPE. This 28-item validated scale derived from a previously published measure showing reliability (Cronbach's $\alpha=.62-.85$, test-retest $r = .46-.89$) and convergent validity with several established coping measures (Carver, Scheier, & Weintraub, 1989) will be used to identify coping strategies consistent with cognitive-behavioral skills, such as positive reframing, and absence of avoidance (Carver, 1997).

Pittsburgh Sleep Quality Index (PSQI). The PSQI assesses sleep quality, which is a critically important covariate of hair cortisol and mood. The PSQI is well-established questionnaire for assessing sleep quality, duration and disturbances. The PSQI shows good internal consistency Cronbach's $\alpha=.83$, test-retest reliability ($r = .85$) and predicted clinically determined poor sleepers at sensitivity of 89.6% and specificity of 86.5% (Buysse, Reynolds, Monk, Berman & Kupfer, 1989). The PSQI reliability and validity has been established with a pregnant sample as well (Skouteris, Wertheim, Germano, Paxton & Milgrom 2009). Unlike the other outcome measures, the Pittsburgh Sleep Quality Index is only measured at baseline.

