The intervention's impact on the study's primary outcomes will be evaluated using intent-to-treat analysis with multiple imputation for missing follow up cases. Outcomes, adjusting for baseline variables, will be analyzed using ANCOVA for continuous variables (self-efficacy, partner support, and coping) and logistic regression for categorical variables (exclusive breastfeeding). To examine the extent in which increased partner support, and lower levels of stress would explain the effects of the intervention, two criteria will be used to establish whether there is statistically significant mediation in the model (MacKinnon, Lockwood, Hoffman, West, & Sheets, 2002; MacKinnon, Fairchild, & Fritz, 2007) including the joint significance of paths a (i.e., the path from predictor to mediator) and b (i.e., the path from mediator to outcome variable) and the asymmetric distribution of the product confidence interval test for the product ($a*b$) of the coefficients a and b , which have both shown the best combination of power and avoidance of type 1 error compared to 12 alternative tests of mediation (MacKinnon et al., 2002; MacKinnon et al., 2007).

We will use the regression-based approach described by Hayes to develop models that allow us to evaluate mediation (Hayes, 2008). The bootstrapping resampling method available in this approach provides an opportunity to run analyses that will approximate the sampling distribution to obtain confidence intervals (CIs) when variables are not normally distributed. With regards to aims 3 and 4, regression (logistic regression for dichotomous outcome variables) analyses controlling for relevant covariates will be used to examine relations between hair cortisol levels and partner support, coping, self-efficacy, and breastfeeding rates. Because both high and low levels of cortisol have been indicated as signs of dysregulation (Miller, Chen, & Zhou, 2007), a quadratic term will be added to the model to examine non-linear relationships. In addition, to these analyses, we will also use the mediation approach described above to explore the extent to which maternal mood may mediate the relations between cortisol and breastfeeding behaviors.

III. REFERENCES

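### Measures calls the primary breastfeeding outcome continuous and not dichotomous, the analysis section treats it as categorical, and the four feeding levels omit breast milk with non-formula food or drink

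*Combined protocol and SAP*

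**What the plan says.** The Introduction sets the endpoint: "Exclusive breastfeeding as well as breastfeeding self-efficacy will be measured at 6 weeks and 6 months as primary outcomes".

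Section II.C.1 (Measures, Index of Breastfeeding Status) describes the instrument. It opens "Rather than conceptualizing breastfeeding as a dichotomous outcome" and says that exclusivity "will be measured as a continuous variable differentiating among exclusive, partial, and token breastfeeding". Mothers choose the "level that accurately described their breastfeeding behaviors within the previous 24 hours". The choices are then set out: "Four levels will be reported: exclusive breastfeeding (breast milk only), partial breastfeeding (breast milk and at least 1 bottle of formula per day"), followed by token breastfeeding (for comfort, not nutrition) and none. Higher values mean more exclusive feeding. In the measures table this index is the only measure of breastfeeding status, and mothers complete it at 0-2 days, 6 weeks and 6 months.

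Section II.E (Statistical Analysis) plans "ANCOVA for continuous variables (self-efficacy, partner support, and coping) and logistic regression for categorical variables (exclusive breastfeeding"). For Aims 3 and 4 it plans regression, with "logistic regression for dichotomous outcome variables", in models that include breastfeeding rates.

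Two further statements bear on the levels. Section II.D.3 sends the follow-up surveys six weeks and six months after the first message. The Introduction notes: "Major health organizations recommend exclusive breastfeeding for at least the first six months postpartum".

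**The concern.** There are two separate matters.

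**Scale of the outcome.** A reader of Measures would expect the index to be analysed as a score. A reader of Statistical Analysis would expect a binary contrast. These answer different questions: a score credits movement from no breastfeeding to partial, and a binary exclusive outcome does not. For a primary outcome, the variable that enters the model should be stated once and in one way before data are seen.

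**Coverage of the levels.** If a mother's feeding pattern matches none of the four descriptions, she has to classify herself. Feeding detail that was not asked for cannot be recovered later. If some of these mothers choose the exclusive level, the reported exclusive rate is too high.

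**Working it through.** The plan gives no exclusive-breastfeeding rate or effect size for this outcome, so there is no figure of its own to reproduce. Its 64 per arm (II.A) is not tied to a named outcome and is not used here.

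**Step 1: the descriptions side by side.**

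| Place | Description of the outcome |
|---|---|
| II.C.1, opening | Not dichotomous; continuous |
| II.C.1, levels | Four ordered categories, top level breast milk only |
| II.E, continuous list | Self-efficacy, partner support, coping; breastfeeding absent |
| II.E, categorical list | Exclusive breastfeeding, logistic regression |
| Introduction | The trial's stated purpose is to raise exclusive breastfeeding rates |
| II.B, Aim 1 and Hypothesis 1 | Breastfeeding rates; more exclusive breastfeeding |

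The opening of II.C.1 is the outlier. The four levels are ordinal, so the label continuous does not fit even within that paragraph. Everything else points to the top level versus the other three, but no sentence says so.

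**Step 2: do the levels cover every infant?** Take an infant given breast milk for nutrition plus solids, water or juice, and no formula, in the previous 24 hours.

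- Exclusive: no, because intake is not breast milk only.
- Partial: no, because there was no bottle of formula.
- Token: no, because feeding was for nutrition.
- None: no.

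No level fits as described. The last survey arrives at or just after the six-month minimum of exclusive breastfeeding cited in the Introduction, so the case is most plausible then.

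**Step 3: what misclassification would do (illustration only).** Let *e* be the true exclusive rate, *u* the share of mothers who fit no level, and *f* the fraction of those who tick exclusive. Then

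reported rate = *e* + *u* × *f*.

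Reported arm difference = true difference + (*u* × *f* in the intervention arm − *u* × *f* in the control arm). If *u* × *f* is the same in both arms, the difference in percentage points is unchanged.

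All inputs are assumptions: true control rate 20% or 30%, true odds ratio 2.0, *f* = 0.5, and equal *u* in both arms. A control rate of 20% has odds 0.25; doubled to 0.50, this gives 33.3%. A control rate of 30% gives 46.2%. For *u* = 10% and a true control rate of 20%, the reported rates are 25.0% and 38.3%, and the odds ratio is (38.3/61.7)/(25.0/75.0) = 1.86.

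| Assumed *u* | Reported rates, true 20% vs 33.3% | Odds ratio | Reported rates, true 30% vs 46.2% | Odds ratio |
|---|---|---|---|---|
| 5% | 22.5 vs 35.8 | 1.92 | 32.5 vs 48.7 | 1.97 |
| 10% | 25.0 vs 38.3 | 1.86 | 35.0 vs 51.2 | 1.94 |
| 20% | 30.0 vs 43.3 | 1.78 | 40.0 vs 56.2 | 1.92 |
| 40% | 40.0 vs 53.3 | 1.71 | 50.0 vs 66.2 | 1.95 |

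Under these assumptions the rate moves more than the comparison. The table does not estimate what will happen in this trial. The only exclusive-breastfeeding percentage in the documents is 44.4% for US women at three months, which settles neither *e* nor *u* at 6 months.

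**Step 4: is there still time?** The study period starts on September 1, 2020 (II.A) and the document is dated 10/05/2020. Adding 42 days gives October 13, 2020 for the earliest 6-week survey. Adding six months gives March 1, 2021 for the earliest 6-month survey. Both fall after the document date.

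**The case against.** **Measurement is not analysis.** Collecting four levels and analysing the top one is ordinary practice. The Measures sentence can be read as rejecting a crude breastfeeding yes/no, like the weekly text question in II.D.4, and not as rejecting exclusive versus not exclusive. Much of this stands. A reader might infer that the primary endpoint is undefined, or that the analyst is free to choose between a score and a binary outcome. The documents do not support that: the stated purpose, Hypothesis 1, the definition of the top level and the analysis section agree. What remains is that Measures rejects a dichotomous *outcome* and calls it continuous, while the analysis section omits it from the continuous outcomes, and the derivation is unwritten.

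**The survey form is not in the documents.** This stands. The real item may be worded more fully, so the coverage point applies to the levels as described.

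**Literal wording already settles the binary outcome.** An infant given solids is not on breast milk only and so is not exclusive. This also stands: error arises only when a mother ticks exclusive because nothing else fits, and nothing in the documents shows how often that would happen.

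**Stronger versions of the coverage point.** A reader might add that a mother who gave only part of a bottle of formula also fits no level. That is over-literal, since partial is the obvious nearest choice. A reader might also infer a spurious treatment effect. Misclassification that is equal in both arms produces none, and the documents give no ground for assuming that it differs by arm.

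**The item has been used before at the site** and is listed among validated measures. That is a cost of changing it, but it does not close the gap.

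**Conclusion.** The point holds in two limited parts.

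1. The Measures and Statistical Analysis sections describe a primary outcome in terms that cannot both be followed. Exclusive versus not exclusive is the clear intended reading, so this is a correction of wording and not a missing endpoint. No figure attaches to it.
2. As described, the four levels leave out breast milk with other food or drink and no formula, mainly a 6-month matter. The possible harm is an inflated exclusive rate. Its size cannot be computed from the documents, and little effect on the arm comparison is expected if the error is equal in both arms. This part rests on the survey item matching the protocol text and on some mothers choosing exclusive for want of a better option.

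Both should be fixed, because the changes are small and feeding detail not collected at 6 months is lost.

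**What to change.** **Wording.** In II.C.1, replace the rejection of a dichotomous outcome and the label continuous with, for example: *Status is collected in four ordered levels; the primary outcome at 6 weeks and 6 months is exclusive (breast milk only in the previous 24 hours) versus not exclusive, by logistic regression adjusted for baseline.* An ordinal analysis of the four levels may be added as supporting, but is optional. The cost is one sentence.

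**Survey item.** First check the REDCap form. If it matches the protocol text, reword the second level at follow-up as *breast milk plus any formula or any other food or drink*, with a tick-box separating formula from other food or drink only. Leave the 0-2 day item unchanged: baseline responses may already exist, and solids should rarely matter at that age. Make the change before 6-month data are collected, and preferably before the first 6-week surveys.

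**Downside.** The follow-up wording departs slightly from that used earlier at the site and at baseline. The tick-box limits this by letting formula feeding be identified separately.

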If the participant meets eligibility, the study staff will describe the study, and interested mothers will identify if they would like to participate together with their partner. If the co-parent is in the room, a study description and consent will occur immediately. If not, the study staff will leave study materials for the mother and co-parent to discuss, and will set a time to return to the room. Only couples in which a partner is able to consent in person and visit the hospital will be included. The study staff member will bring an iPad for the participants to use for completing pre-intervention surveys. All pre-intervention and study surveys will be completed by accessing the REDcap online survey link on the iPad. No survey data will be stored on the iPad or other computer hard-drive. Survey data entered into REDCap via the iPad will be stored in the REDcap's password-encrypted server.

Participants will complete two mood questionnaires: the EPDS and the Mood Screener. Participants whose survey responses suggest they meet criteria for a current depressive episode will be provided with education and treatment resources for area providers. An automatic pop-up message is coded to appear on the iPad survey when a mother or partner's survey indicates anything other than no risk for suicide. The initial surveys are completed on iPad before being randomized to the intervention or usual care group. The research team member who consented the patient will review the completed questionnaire before continuing to introduce the intervention or usual care instructions. The study nurse will collect the initial surveys and check for the coded message as soon as the participant completes the surveys. If a survey shows depression or suicide risks, the study staff will use the following standard OhioHealth protocol. A patient (included or excluded from study) who reports suicidal ideation (a 1, 2, or 3 on question #10 of the EPDS or yes to the suicide items on Mood Screener), an in-hospital behavioral health consult will be arranged by the assigned clinical nurse for further evaluation of suicide risk and treatment need. As mentioned, these policies are consistent with OhioHealth's approach to depression screening (currently using the SAD Persons; scale-Appendix B). Additionally, their primary care physicians will be notified of the patient's condition in order for follow up to occur post discharge.

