Partners will also complete a baseline EPDS and Mood Screener, as part of the baseline survey (not eligibility screening). If partners report suicidal ideation, the level of risk will be assessed by the study staff at the time of survey completion. All cases with low/moderate risk will result in referral to a suicide hotline and immediate mental health referral. High risk

(potential immediate threat) cases will result in an emergency mental health referral (911) made with the participant's knowledge. The details of this risk protocol are attached. If the partner's survey results suggest they meet the criteria for current depressive episode, we will ask them for their primary care provider's contact information so that we can notify them for follow-up. If the patient or partner do not have a primary care provider, we will refer them to the emergency department for evaluation and referral to the appropriate level of care.

The six week and six month surveys will have an automatic message appear at the end of the survey for the mother or partner to read if the suicidal ideation or depression score is elevated. The message states the following: "If your survey results show an elevated depression score you should contact your primary healthcare provider. If your survey suggest you are at risks for suicide or this is an emergency you should contact 911 or the suicide hotline phone number **[name] [name]**. Survey responses will be reviewed by the research team daily and phone contact will be attempted within 24 hours of the survey receipt. Three attempts to reach the participant will be tried within 24-48 hours. The consent form will remind patients and partners that referrals and physician notification may occur to ensure optimal care. Patients will be informed that failure to accept the notification of a health care provider clause will render them ineligible for the study.

3. Randomization and Bias Reduction:

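### At 6 weeks and 6 months the automatic crisis message comes at the end of a remotely completed survey, so a parent who endorses a suicide item and stops early would not see it at that moment

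*Combined protocol and SAP*

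**What the plan says.** **Placement.** Section II.D.2 (Recruitment Procedures) states: "The six week and six month surveys will have an automatic message appear at the end of the survey". It is meant for a mother or partner whose suicidal ideation or depression score is elevated. It points them to their primary provider or, for suicide risk or an emergency, to 911 or a hotline.

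**Delivery.** Section II.C.1 (Measures) and the end of the group-allocation text in II.D.3 both send the follow-up surveys as a REDCap link by email. Measures adds text-message reminders.

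**Content.** The measures table in II.C lists the EPDS and the Mood Screener for both parents at 6 weeks and 6 months. Of the Mood Screener, Measures says "only the assessment for current episodes will be administered at the 6 week and 6 month follow-up time points".

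**Staff response at follow-up.** Exclusion criterion 2e in II.A says that participants identified with suicidal ideation at either follow-up will be assessed further and referred, and may stay in the program. II.D.2 adds: "Survey responses will be reviewed by the research team daily and phone contact will be attempted within 24 hours of the survey receipt", and then "Three attempts to reach the participant will be tried within 24-48 hours".

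**Baseline.** II.D.2 says "An automatic pop-up message is coded to appear on the iPad survey" when a parent's answers show any suicide risk, and staff check for it once the surveys are done. The response rule for mothers is "a 1, 2, or 3 on question #10 of the EPDS or yes to the suicide items on Mood Screener". The paragraph on partners' baseline answers closes with "The details of this risk protocol are attached".

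**The concern.** A message on the last page reaches only those who get to the last page. At baseline a staff member is at the bedside, reviews the answers and verifies completion. At follow-up the parent is at home with a phone or computer. Someone who has just disclosed suicidal thoughts and then closes the survey would leave without the crisis contacts, and any response would depend on staff finding the saved answers.

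The two follow-up surveys are the only mood assessments after discharge in the measures table. The weekly text check-in described in II.D.4 asks only about breastfeeding. The point rests on how serious a single miss could be, not on how often it would happen.

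**Working it through.** No formula in the plan bears on this, so the check is a comparison of the relevant text.

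1. **Is the follow-up survey really remote?** II.D.2 has a general sentence placing study surveys on the iPad, and the data-security text in II.D.4 has a similar one. The first describes the hospital visit. The two statements specific to follow-up (II.C.1 and II.D.3) both say email. The specific statements govern, so the survey is remote.

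2. **Is there an earlier message at follow-up?** II.D.2 gives one placement, the end. No other section describes a message triggered at the suicide items in the 6-week or 6-month survey.

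3. **Does the trigger need the whole survey?** A depression score needs the full scale. The suicide rule used at baseline does not: one answer of 1, 2 or 3 to EPDS question 10, or a yes to a Mood Screener suicide item, is enough. An end placement is therefore natural for the depression part of the message but not needed for the suicide part.

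4. **What follows for a parent who stops early?** If the parent stops after a suicide item and before the end, the message is not reached. If the parent later returns and finishes, it is delayed, not lost.

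5. **Does the staff safeguard cover that parent?** The daily review is of survey responses, a phrase wide enough to include partial ones. The 24-hour contact window runs from survey receipt, which is not defined. Cover for unfinished surveys is thus unstated. It is not shown to be missing.

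6. **How wide is the gap within the survey?** The order is not given. As an illustration only, assume the survey follows the measures table:
   - After EPDS question 10 come the DASS-21 (21 items), the Mood Screener (9 symptoms) and the acceptability scale (11 questions): 21 + 9 + 11 = 41 items, plus open-ended responses.
   - After the Mood Screener comes only the acceptability scale: 11 questions plus open-ended responses.
   - If the suicide items come last, almost nothing follows them and the gap nearly disappears.

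7. **Scope.** 2 follow-up times x 2 parents = 4 follow-up surveys per couple. The documents give neither a rate of positive suicide items nor a rate of unfinished surveys, so no expected count can be formed.

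**The case against.** The strongest reply is that the on-screen message is a supplement. The plan's main follow-up response is human: further assessment and referral (II.A), daily review and phone contact (II.D.2). This stands. A reader might infer that a parent who stops early has no safety net, or that unfinished surveys fall outside the review. The documents support neither reading. They are silent on partial surveys, and the attached risk protocol, which might settle the matter, was not available to check. What the staff response cannot do is put the hotline in front of the parent at the moment of disclosure.

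A reader might also infer that baseline has an item-level warning which follow-up drops. That is not supported either. II.D.2 does not say where in the baseline survey the pop-up appears, and staff look for it after the surveys are complete, so it too may come at the end. It shows only that a response-triggered message can be coded. The clear baseline difference is staff presence, which an earlier message would not restore.

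Other mitigating facts also stand:
- Mothers with a current depressive episode, depression treatment or suicide risk at the initial survey are excluded, though partners are not.
- Text reminders and a $25 card for each completed follow-up survey encourage finishing.
- Pilot follow-up at 6 weeks was 94% of mothers and 90% of partners. That pilot was very small (17 mothers and 10 partners), these are follow-up rates and not survey-completion rates, and the trial itself plans for 25% attrition.

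**Conclusion.** The point holds in a limited form. The plan places the automatic crisis message at the end of a survey completed away from staff, so a parent who endorses a suicide item and stops before the end would not see it then. That follows from the text and needs no assumption about rates.

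The number affected is unknown and probably small. For the staff response to fail as well, the parent would have to not return to finish, and the daily review would have to miss the saved answer. The practical size depends on the unstated order of the questionnaires and on whether partial answers are saved and reviewed. Because moving part of the message is so easy and the possible harm so serious, the change is worth making as a cheap improvement of optional to moderate priority. It has no bearing on power, error rates or the analysis.

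**What to change.** In the II.D.2 paragraph on the follow-up surveys:

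1. Show the same message to either parent directly after the suicide items as well as at the end. Trigger it with the rule already used for mothers at baseline: 1, 2 or 3 on EPDS question 10, or yes to a Mood Screener suicide item. Keep the questionnaire order.
2. While editing, state that saved partial responses are part of the daily review, and say what counts as survey receipt for the 24-hour window. If this is already the practice, it is one clarifying sentence.

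The cost is minor survey configuration and one or two protocol sentences. An automatic staff alert on a saved positive answer would be a further step, but the documents do not show whether this REDCap set-up can do that, and the earlier message does not depend on it.

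The plan says of consent: "The consent form will remind patients and partners that referrals and physician notification may occur to ensure optimal care". Whether that wording extends to answers in an unfinished survey could not be checked, so the sponsor should confirm it. The downside of the change is that the message may come before any scales placed after the suicide items, which could affect how those scales are answered. Reviewing partial surveys may also add a few staff calls.
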